6 SUBJECT ACCOUNTABILITY AND DISPOSITION

The following subject data will be summarized and presented by treatment group (roxadustat and active control) unless specified otherwise:

- Number and percentage of subjects screened (overall only) and randomized (using the screened subjects population)
- Number and percentage of subjects screened (overall only) and randomized (using the screened subject population) in the original protocol and amendments.
- Number and percentage of subjects randomized at each center, and for all centers combined, by treatment group (using the ITT population)
- Number and percentage of subjects in each analysis set, by treatment group (using the ITT population)
- Number and percentage of subjects excluded from the Per Protocol analysis set by reason for exclusion, treatment group (using the ITT population)
- Kaplan-Meier plots will be generated for premature treatment discontinuation by randomization arm showing 2 curves (one curve per treatment group).
- All subjects who prematurely discontinued during the Treatment Period will be listed by discontinuation reason for the ITT population.

7 DEMOGRAPHICS AND OTHER BASELINE CHARACTERISTICS

Demographic parameters and important baseline disease characteristics will be summarized by treatment group for the ITT, Safety, FAS and PPS populations. These include but may not be limited to age, age group (18 to 64, 65 to 74, ≥ 75), sex, ethnicity, race, region, weight, body mass, by stable dialysis and newly initiated dialysis, index (BMI), hemoglobin (the mean of the two most recent central lab results), platelets, mean hemoglobin category (≤ 10.5 g/dL or > 10.5 g/dL), mean weekly baseline ESA (EPO or EPO equivalent) dose per kilogram category (≤ 150 IU/kg/week or > 150 IU/kg/week) in the 4 weeks prior to randomization, mean ESA (EPO or EPO equivalent) in 4 weeks (if on epoetin or darbepoetin) or in 8 weeks (if on Mircera) prior to randomization category ($< 5,000$ IU/week, 5,000 to 8,000 IU/week, $> 8,000$ to 16,000 IU/week, $> 16,000$ IU/week), ferritin, ferritin group (< 100 , 100- < 400 , ≥ 400 ng/mL), TSAT and TSAT group (< 20 , 20- < 40 , $\geq 40\%$), iron deplete (ferritin < 100 or TSAT $< 20\%$) vs. not, baseline C-reactive protein (CRP) group (CRP \leq ULN vs. CRP $>$ ULN), and history of cardiovascular disease or cerebrovascular disease or thromboembolic disease (Yes or No), primary reason for CKD/ESRD (DM and HPT vs. all others).

Descriptive statistics (n, mean, standard deviation, median, minimum, and maximum) will be presented for continuous variables. In addition, 25%-75% values of hemoglobin and platelets will be presented. Frequency distributions (number and percentage of subjects) will be presented for categorical variables.

Descriptive statistics of baseline values for other parameters will be presented in their change from baseline tables.

8 MEDICAL HISTORY

Medical history will be coded using Medical Dictionary for Regulatory Activities (MedDRA). Medical History of interest including chronic kidney disease (CKD) History inclusive of CKD cause, cardiovascular disease including dyslipidemia, cerebrovascular disease, thromboembolic history, hypertension history, diabetes history, and anemia history will be summarized by system organ class, preferred term and treatment group for the Safety Population.

9 STUDY MEDICATION

9.1 Extent of Exposure

Exposure to study medication will be summarized by treatment group in terms of treatment duration in weeks, which is calculated using the following formula: (the last dose date of study medication taken - the first dose date of study medication taken +1)/7.

Total weekly study drug exposure is defined as the total prescribed dose (in mg and mg/kg for roxadustat and IU and IU/kg for ESAEPO) of study drug administered within the week (windowed by 7-day period from Day 1).

Duration of exposure, weekly exposure and total study drug exposure will be tabulated by treatment group for the safety population.

Per dose amount and dosing frequency will also be tabulated by treatment group for the safety population and PPS population.

Patient-Exposure-Year (PEY) is defined as Last Dose Date – First Dose Date + 1.

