- Duration of treatment or days in treatment is calculated as: last dose date of study medication – first dose date of study medication + 1
- Body weight, height and temperatures will converted using the following formula:
 - kg = lb/2.2
 - cm = 2.54 x in
 - C° = (5/9) x (F° – 32)
- The mean, standard deviation and median will be presented with adding one more decimal to raw data with rounding off. The minimum and maximum will be presented with the same number of decimals as in the raw data.
- All percentages will be rounded to one decimal place and lined up by the decimal place. The percentage will be suppressed when the count is zero.
- Any p-values will be rounded to four decimal places and will be presented as '<.0001' if they are less than 0.0001 after rounding.
- All tables and listings will have a header showing "FibroGen, Inc.", the protocol number, and Page x of y. Footer will indicate the program file path/name, run date and run time.
- For continuous variables that are recorded as "< X" or "> X", the value of "X" will be used in the calculation of summary statistics. The original values will be used for the listings.
- Decimal points will be presented as follows: N will be presented without decimal, minimum and maximum in same precision as in the database, mean and median in one

more decimal than minimum and maximum, and SD and SE in one more decimal than mean and median.

- Tables and figures will use derived analysis visit. Listings will use nominal visits, show the flag to indicate analysis visit to be used. Namely, both Nominal visit and analysis visit will be presented in the listing.
- Additional data handling conventions are detailed in Appendix 5.
- Analysis visits assigned for hemoglobin samples collection corresponding to the range of treatment days (window) during which an actual visit may have occurred are presented in Appendix 5. All scheduled and unscheduled hemoglobin samples that belong to each window will be taken into account.

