11.3.2 Hospitalizations

Hospitalizations are collected in the Hospitalization Records Form of the eCRF. For each subject, an entry will be recorded for each hospitalization. The days of hospitalization will be calculated as the sum of all hospitalizations durations in days (Date of discharge – Date of Admission + 1). In case of missing dates, the hospitalization duration will be assumed to be 5 days.

Only hospitalizations with admission dates that occur during the Treatment Period and up to 7 days after the last study medication date will be taken into account.

The following hospitalization-related data will be analyzed and compared between the 2 treatment groups:

- Time to first hospitalization (% of subjects) up to Week 52, 7 days after last dose.
- Time to first hospitalization or skilled nursing facility (% of subjects) up to Week 52, 7 days after last dose.
- Number of days of hospitalizations
- Number of days of medical-facility
- Number of days of hospitalizations per patient-exposure year (PEY).
- Number of days in hospital or skilled nursing facility per patient-year exposure (PEY).
- Number of days of medical-facility (hospital, skilled nursing facility, emergency room, or overnight observation) per subject-exposure year (PEY).
- Number of days on treatment out of hospital and skilled nursing facility up to Week 52, 7 days after Last Dose.

Note: Sensitivity analysis may be performed by excluding elective procedures using only hospitalization due to AE

The time to hospitalization event will be compared between the two treatment groups using cox model including baseline stratification factors. The proportion of subjects hospitalized will be compared between the 2 treatment groups using logistic regression model and stratified by the baseline stratification factors. The mean number of days of hospitalization will be analyzed and compared between the 2 treatment groups using the Mantel-Haenszel mean score test adjusting for stratification factors.

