11.3.3.1 Red Blood Cell Transfusion

For a subject receiving RBC or whole blood transfusion, the Time at Risk (time up to first use) will be calculated (in years) as:

$$(\text{First use of transfusion date} - \text{First dose date of study medication} + 1) / 365.25$$

For a subject not receiving transfusion, the Time at Risk (time until they get censored) is calculated as:

$$(\text{Date of last study medication} - \text{First dose date of study medication} + 1) / 365.25$$

The red blood cell transfusion form of the eCRF in the cumulative visit will be used to derive the number of RBC packs. The number of RBC units is collected in this form. For transfusions where the number of units is not given but the volume transfused is given, the number of units will be estimated by dividing the volume transfused by 250 mL (for transfusion of packed cells) or by dividing the volume transfused by 500 mL (for transfusion of whole blood).

The total number of RBC units/packs during the Treatment Period is calculated for each subject by the sum of the transfused units between the Analysis Date of First Dose and up to the Analysis Date of Last Dose. The following 2 endpoints will be analyzed:

- Proportion of subjects who receive RBC transfusions. The proportion of subjects who received RBC transfusion will be compared between the 2 treatments using logistic regression model adjusting for baseline hemoglobin as covariate and treatment group and stratification factors as fixed effects.
- Number of RBC packs per subject-month exposure to study medication. The mean number of RBC packs will be compared between the 2 treatment groups using ANCOVA model adjusting for baseline hemoglobin as covariate, treatment group, and stratification factors as fixed effects.

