12.1 Adverse Events

Adverse events will be coded using the latest MedDRA version. An AE (classified by preferred term) started during the Treatment Period will be considered a treatment-emergent adverse event (TEAE) if it was not present prior to the first dose of study medication, or it was present prior to the first dose of study medication but increased in severity during the Treatment Period up to 7 days after last dose of study drug or until the administration of another anemia drug (other than the randomized treatment). An AE that occurs more than 7 days after study medication or after the administration of another anemia drug (other than the randomized treatment) will not be counted as a TEAE.

The number and percentage of subjects reporting TEAEs in each treatment group will be tabulated by system organ class and preferred term; by system organ class, preferred term, and severity; and by system organ class, preferred term, and relationship to study medication. If more than one event occurs with the same preferred term for the same subject, the subject will be counted only once for that preferred term using the most severe and most related occurrence for the summarization by severity and by relationship to the study medication. The distribution of TEAEs by severity and relationship to study medication will be summarized by treatment group.

The incidence of common ($\geq 5\%$ of subjects in any treatment group) TEAEs, treatment-emergent serious AEs (TESAE), and AEs leading to discontinuation of study medication will be summarized by SOC, preferred term and treatment group, sorted in decreasing frequency for the test treatment. In addition, the incidence of death and fatal SAEs (i.e., events that caused death) will be summarized separately by treatment group, SOC and preferred term. Treatment emergent adverse events of interest will also be reported in terms of incidence rate per Patient Exposure Year (PEY).

Discontinuation of study medication due to worsening anemia based on hemoglobin value (lack of efficacy) will not be counted under AEs leading to discontinuation.

Listings will be presented of subjects with serious adverse events (SAEs), subjects with adverse events leading to discontinuation, and subjects who died.

Temporal profile of TEAEs of special interest may also be plotted by treatment group showing the subjects in the y-axis and time to these TEAEs in the x-axis (Appendix 8).

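### SAP 9.1 defines patient-exposure-years as a count of days ending at last dose, while the events divided by it are counted over a different window

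*SAP*

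**What the plan says.** SAP 9.1 gives the definition: "Patient-Exposure-Year (PEY) is defined as Last Dose Date" minus first dose date plus 1, with no divisor. Neither document gives another formula. The protocol lists the abbreviation and reports rates per PEY but does not say how PEY is calculated.

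Elsewhere the SAP shows the divisor when it wants a unit other than days:

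- Treatment duration in weeks, in the same section: "the last dose date of study medication taken - the first dose date of study medication taken +1)/7".
- Transfusion analysis, SAP 11.3.3.1: "the Time at Risk (time up to first use) will be calculated (in years) as" a date difference plus 1, divided by 365.25.
- SAP 5.4: "Duration of treatment or days in treatment is calculated as" last dose date minus first dose date plus 1, which is the PEY expression under a label of days.

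Three families of rates use PEY, and each counts events past last dose:

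- Adverse events, SAP 12.1: "Treatment emergent adverse events of interest will also be reported in terms of incidence rate per Patient Exposure Year (PEY"). Counting runs "up to 7 days after last dose of study drug or until the administration of another anemia drug" other than the randomized treatment.
- Hospital and other facility days, SAP 4.3 and 11.3.2. The counting rule is "Only hospitalizations with admission dates that occur during the Treatment Period and up to 7 days after the last study medication date".
- Missed-dialysis days, SAP 4.3 and 11.3.3, with sessions counted up to 7 days after last dose.

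**The concern.** Two things do not fit. First, a quantity named in years is computed in days, so a program that follows the text returns rates on the wrong scale. Second, numerator and denominator cover different periods. Exposure stops at last dose, while events are counted for up to 7 days more. In the other direction, adverse-event counting can close when another anemia drug is given, while exposure keeps accruing.

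What is at stake is the absolute level of the reported rates. A reader of the study report would set adverse-event and hospitalization rates per PEY beside those of other trials, and that use depends on both the unit and the window.

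**Working it through.** The documents print no PEY total and no rate, so there is no figure of the plan's own to reproduce. The check applies the definitions. Let D = last dose date − first dose date + 1, in days.

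**Units**

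- PEY as written = D.
- PEY in years, to last dose = D/365.25.
- At D = 364 (52 weeks): as written 364; in years 364/365.25 = 0.9966.
- The denominator is 365.25 times too large, so the rate is 365.25 times too small. The factor is the same in both arms and cancels from any ratio.

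**The 7 days after last dose**

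Time matched to a window that stays open for all 7 days is (D + 7)/365.25. Using D/365.25 instead multiplies the rate by (D + 7)/D, an overstatement of 7/D. For an arm as a whole, D is its mean exposure.

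| Exposure | D (days) | 7/D |
|---|---|---|
| 2 weeks | 14 | 50% |
| 4 weeks | 28 | 25% |
| 8 weeks | 56 | 12.5% |
| 26 weeks | 182 | 3.8% |
| 52 weeks | 364 | 1.9% |
| 104 weeks | 728 | 0.96% |
| 156 weeks | 1092 | 0.64% |

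These are upper limits for adverse events, because the window can close before day 7.

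**Both together.** Assume 100 subjects with 364 days each and 10 events:

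- As written: 10/36,400 = 0.000275 per PEY.
- Divided by 365.25: 10/(36,400/365.25) = 0.1003, or 10.03 per 100 PEY.
- With the 7 days added: 10/(37,100/365.25) = 0.0985, or 9.85 per 100 PEY.

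The two errors run in opposite directions: the missing divisor lowers the rate and the missing 7 days raise it.

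**Effect on a between-arm ratio.** The 7 days matter only if mean exposure differs. With W weeks of exposure the factor is 1 + 1/W, so the distortion is (1 + 1/W₁)/(1 + 1/W₂). For assumed means:

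- 78 against 104 weeks: 1.003
- 52 against 104 weeks: 1.010
- 4 against 52 weeks: 1.23

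**Window closed early by another anemia drug.** SAP 12.1 does not count adverse events after such a drug is given. SAP 3.2 and protocol 4.6.3.2 allow a roxadustat subject to resume study drug after ESA rescue. Assume rescue at week 20 and last dose at week 104. Read literally, events are counted over about 140 days and divided by 728 days of exposure, so that subject's denominator is 728/140 = 5.2 times too long. The trigger is not the same in both arms: any ESA closes the window for a roxadustat subject, but only a different agent does so for an epoetin alfa subject. The documents do not say how many subjects this would affect.

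**Contrast.** RBC units in SAP 11.3.3.1 are summed from first to last dose only, so that numerator does stop with exposure. Transfusion time at risk already carries the divisor. Neither is affected.

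**The case against.** The strongest reply is that this is a slip of notation. The quantity is called a year, the SAP shows the conversion in 11.3.3.1, and the table specifications sit in a separate document that may state the unit. A 365-fold error would be obvious in any output. This bears on how likely the error is to reach a report, and it stands to that extent. It does not alter what SAP 9.1 instructs.

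It can also be said that dividing by drug exposure is a legitimate choice, since the term is exposure-year and it sits under extent of exposure. That is fair for describing exposure. It does not settle the denominator of a rate whose numerator runs over another window.

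No primary or ranked secondary endpoint uses PEY. The Mantel-Haenszel tests in SAP 11.3.2 and 11.3.3 are described on mean numbers of days, adverse-event rates per PEY carry no test, and adjudicated cardiovascular safety follows a separate pooled plan. All of this stands, and it confines the point to descriptive rates.

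A reader might go further and infer that the 7-day gap biases the comparison because events cluster around discontinuation, or because one arm has shorter exposure. The documents support neither statement. The larger percentages in the table also need a mean exposure of a few weeks. The planned minimum is 52 weeks, although it may be shortened for subjects enrolled under Amendments 1 and 2, and some subjects will stop early.

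**Conclusion.** The point holds, at modest weight. As written, PEY is in days. If it is programmed that way, absolute per-PEY rates are 365.25 times too small, with ratios between arms unchanged. It does not follow that the reported rates will be wrong by that factor; that depends on literal programming, and the name itself invites a correction.

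Once the units are right, the missing 7 days overstate rates by about 1.9% at a mean of 52 weeks and 0.96% at 104 weeks, assuming every subject's window stays open for the full 7 days. Any distortion of a rate ratio from this source needs unequal exposure, and was 1% or less in the assumed cases of 52 or 78 against 104 weeks.

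For subjects who receive another anemia drug and continue study drug, the denominator is too long by an amount that depends on timing. Its total effect cannot be sized from the documents. No confirmatory conclusion depends on any of this.

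**What to change.** In SAP 9.1, define PEY = (last dose date − first dose date + 1)/365.25 and keep it for describing drug exposure, so that it still agrees with treatment duration.

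For rates, add a separate quantity: time at risk = (min(last dose date + 7, end of that event's counting window) − first dose date + 1)/365.25. For adverse events the window ends at another anemia drug if that comes first. Use this denominator in SAP 11.3.2, 11.3.3 and 12.1.

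Adding 7 days does not fully align hospital-day rates, because SAP 11.3.2 limits only the admission date and counts days through to discharge. Either truncate the counted days at the end of the window, or state that days after it are included.

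The cost is one corrected line, one added definition and one sentence on hospital days. No new data are needed, and no primary or ranked secondary analysis changes.

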9.1.1 Dosing Changes

Dosing changes for both treatment groups are collected in the Study Drug Administration/ Dose Adjustment Form in the eCRF. Two types of dosing changes will be calculated.

A dose-per-intake change is the change in the number of milligrams on the intake day (for example from 200 mg TIW to 250 mg TIW). A weekly-dose change is the change in the prescribed weekly dose, calculated as the dose-per-intake times the weekly frequency.

For example a change from 200 TIW to 250 TIW is a change of 600 mg to 750 mg per week which is considered as a change in dose-per-intake and a change in weekly-dose as well.

For each subject the total number of dose-per-intake changes and the weekly-dose changes will be calculated for safety and PPS population.

9.1.2 Duration of Exposure

Exposure time will be categorized according to the following categories by treatment arm (roxadustat and ESA) for safety and PPS population:

- Less than 2 weeks
- At least 2 weeks, less than 4 weeks
- At least 4 weeks, less than 26 weeks
- At least 26 weeks, less than 52 weeks
- At least 52 weeks, less than 78 weeks
- At least 78 weeks, less than 104 weeks
- At least 104 weeks, less than 130 weeks
- At least 130 weeks, less 156 weeks
- More than 156 weeks
- Unknown

9.2 Treatment Compliance

Study medication dosing compliance for a specified period is defined as the total dose (mg or IU) actually taken by a subject during that period divided by the prescribed dose expected to be taken during the same period multiplied by 100.

An overall per-dose compliance measure can be calculated by $(\# \text{ of actual dose administrations}) / (\text{Total } \# \text{ of expected dose administrations}) * 100$ during the subject's Treatment Period. Descriptive statistics for study medication compliance will be presented by treatment group for the entire Treatment Period of the study for safety population.

Compliance will be summarized as follows:

- Descriptive statistics will be summarized by the 2 treatment groups.
- Percent compliance will be categorized according to the following categories by treatment groups:
 - less than 50% (significant drug noncompliance)
 - at least 50%, less than 75% (moderate drug noncompliance)
 - greater or equal 75% (drug compliance)
 - unknown

10 PRIOR AND CONCOMITANT MEDICATIONS

The World Health Organization Drug Dictionary (WHODD) will be used to classify prior and concomitant medications by therapeutic class and generic name based on ATC code level 3. Prior medication is defined as any medication taken and stopped prior to the first dose of the study medication within 30 days before signing the informed consent. Concomitant medication is defined as any medication taken between the day of first dose of the study medication and the day of ET/EOT Visit date + 28 days, inclusive.

Medication start and end dates will be compared with the start date of study drug and classified as per Table 4.

In case of partial or missing dates, comparisons will be made based on the level of detail available. For example, if start date of study drug is 04Jan2013, and a medication has a start date of 04Jan2013, the medication will be classified as concomitant. A start date of Jan2013 (i.e., missing day) would also see the medication classified as concomitant.

Table 4. Classification of Prior and Concomitant Medications

Start date \ End date	Before start of study drug administration	On or after start of study drug administration	Missing
Before start of study drug administration	Prior	Concomitant	Concomitant
On or after start of study drug administration	–	Treatment Emergent Concomitant	Treatment Emergent Concomitant
Missing	Prior	Concomitant	Concomitant

Both prior and concomitant medication usage will be summarized by the number and proportion of subjects in each treatment group. Subjects will only be counted one time in each unique ATC Class and generic name if multiple drugs are used by a subject.

Detailed analyses may be performed on prior and concomitant medications of special interests such as oral iron, blood pressure medications and lipids medications.

